6.12 End of Trial Treatment (EOT) Visit

Post C8D1, patients experiencing clinical benefit with no evident disease progression will be given the opportunity to enroll in an open-label compassionate use study protocol and will be followed up. Excluding patients who participate in the compassionate use study protocol, all other patients will undergo the end-of-treatment (EOT) assessments within 7 days after the last dose of study drug or discontinuation from the study. Radiological assessment and bone marrow biopsy will not be performed if done earlier within 28 days.

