6.13 End of Study (EOS) Visit

All patients must be followed up telephonically for adverse events for 30 calendar days after the last dose of study drug. In case of drug related SAE/AE or treatment discontinuation due to adverse event, the subjects will be followed till the resolution/stabilization of the AE or 30 days after the last study dose whichever is the earlier

Table 5: Schedule of Events for Dose Escalation

	Screening	Cycle 1					Cycle 2				Cycle 3			Cycle 4-7			EOT ²⁴ /C8D1	EOS ²⁵
Day	D-28 to 0	D1	D3	D8	D15	D22	D1	D8	D15	D22	D1	D8	D15	D1	D8	D15	D1	-
Window period	-28	0	-	±1	±1	±1	±1	±1	±1	±1	±1	±1	±1	±1	±1	±1	+7	+30
Study Days	D-28 to 0	1	3	8	15	22	29	36	43	50	57	64	71	-	-	-	197	227
Informed Consent ¹	X	-	-	-	-	-	-	-	-	-	-	-	-	-	-	-	-	-
Demographics ²	X	-	-	-	-	-	-	-	-	-	-	-	-	-	-	-	-	-
Medical history ³	X	-	-	-	-	-	-	-	-	-	-	-	-	-	-	-	-	-
Vitals ⁴	X	X	-	X	X	X	X	X	X	X	X	X	X	X	X	X	-	-
Height and weight ⁵	X	X	-	X	X	X	X	X	X	X	X	X	X	X	X	X	-	-
Complete Physical exam ⁶	X	-	-	-	-	-	-	-	-	-	-	-	-	-	-	-	-	X
Abbreviated Physical exam ⁶	-	X	-	X	X	-	X	X	X	-	X	X	X	X	X	X	-	-
ECOG Performance Status	X	X	-	-	-	-	-	-	-	-	X	-	-	-	-	-	X	-
Tumor staging	X	-	-	-	-	-	-	-	-	-	-	-	-	-	-	-	-	-
Laboratory assessment																		
Complete blood count ⁷	X	X	-	X	X	X	X	X	X	X	X	X	X	X	X	X	-	-
Chemistry panel I ⁸	X	X	-	X	X	X	X	X	X	X	X	X	X	X	X	X	-	-
Chemistry panel II ⁹	X	X	-	-	-	-	-	-	-	-	X	-	-	X	-	-	X	-
Serology ¹⁰	X	-	-	-	-	-	-	-	-	-	-	-	-	-	-	-	-	-
PT and INR ¹¹	X	X	-	X	X	X	X	X	X	X	X	X	X	X	X	X	-	-
Urinalysis (routine)	X	X	-		X	-	X	-	X	-	X	-	X	-	X	-	X	-
Pregnancy test ¹²	X	X	-	-	-	-	X	-	-	-	X	-	-	X	-	-	X	-
12-lead ECGs ¹³	X	X	-	X	X	-	X	-	-	-	X	-	-	X	-	-	X	-
Pharmacokinetic samples ¹⁴	-	X	-	X	-	-	X	-	-	-	X	-	-	X	-	-	-	-
Bone marrow biopsy ¹⁵	X	-	-	-	-	-	-	-	-	-	-	-	-	-	-	-	-	-

Skin biopsy ¹⁶	X	-	-	-	-	-	-	-	-	-	-	-	-	-	-	-	-
Disease assessment																	
Radiological scan/imaging ¹⁷	X	-	-	-	-	-	-	-	-	X	-	-	-	-	-	X	-
mSWAT ¹⁸	X	-	-	-	-	-	-	-	-	X	-	-	-	-	-	X	-
Skin photographs ¹⁹	X	-	-	-	-	-	-	-	-	-	-	-	-	-	-	-	-
Correlative markers ²⁰	X	-	-	-	-	-	-	-	-	X	-	-	-	-	-	-	-
Treatment administration																	
Tenalisib ²¹	-	-	X	X	X	X	X	X	X	X	X	X	X	X	X	-	-
Romidepsin infusion ²²	-	X	-	X	X	-	X	X	X	-	X	X	X	X	X	-	-
Drug compliance	-	X	-	X	X	X	X	X	X	X	X	X	X	X	X	X	-
Safety evaluation																	
AE evaluation ²³	X	X	-	X	X	X	X	X	X	X	X	X	X	X	X	X	X
SAE evaluation	X	X	-	X	X	X	X	X	X	X	X	X	X	X	X	X	X
Concomitant medication	X	X	-	X	X	X	X	X	X	X	X	X	X	X	X	X	X

Foot notes:

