1. Patient should be re-consented, if informed consent is obtained >30 days prior to the initiation of trial treatment. The first day of Romidepsin administration will be considered the initiation of treatment (C1D1).
2. Demographic profile will include age, sex and race.
3. Detailed history will be taken at screening that includes history of cancer, past history, no of prior therapies and prior medication (in last 4 weeks); and other medical history. Any medical significant history at subsequent visit will be captured as adverse event.
4. Vitals will be done prior to the administration of study treatments (Pre-dose and Pre-infusion), during infusion and post-infusion as applicable, at the time points specified above.
 - In the first cycle, vitals will be taken prior to the administration of study treatments (15 min before Tenalisib dose and 5 min prior to infusion). During the infusion, vitals should be done at every 15 min (\pm 5 min) during first hour and at every 30 min (\pm 10 min) for next 3 hours and 1 hr (\pm 15 min) post infusion. All time points will be recorded in the CRF.
 - In subsequent cycles, vitals will be done as per the institutional practice. Pre-dose; and Pre- and Post-infusion vitals will be recorded in the CRF.
 - When slowing or re-starting an infusion due to an infusion reaction, vital signs should be monitored at every 15 minutes or as directed by the investigator until the infusion is completed and 15, 30 and 60 min post-infusion and longer if necessary until the subject is stabilized. In such case, the event of infusion reaction should be recorded as an adverse event.
5. Weight will be measured at all visits. Height to be recorded at screening only; historical data is acceptable.
6. Physical examination will include lymph node and systemic examination. Complete physical examination will be done at screening and EOT visits. At other visits, abbreviated examination (directed physical examination) will be done depending on the assessment of tumor.

7. Complete blood count: Hb, complete blood count, total leucocyte and differential count and platelet count. Additional investigations will be performed if clinically indicated. Hematology must be done \leq 7 days prior to C1D1. However, if these initial examinations are obtained within 72 hours of C1D1; they do not have to be repeated.

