- 22. Romidepsin will be administered as an intravenous infusion over 4 hours unless progression of disease or toxicity warranting discontinuation of therapy.
- 23. All AEs regardless of seriousness or relationship to study drug should be recorded spanning from the informed consent drug until 30 calendar days after the last dose of study drug.
- 24. Post C8D1, *patient experiencing clinical benefit* with no evident disease progression will be given the opportunity to enroll in an open-label compassionate use study protocol and will be followed up. Excluding patients who participate in compassionate use study protocol, all other patients will undergo the end-of-treatment (EOT) assessments within 7days after the last dose of study drug or discontinuation from the study.
- 25. Patients should be followed for AEs for 30 calendar days after the last dose of study treatment. Telephonic follow up during this period is acceptable. All new AEs occurring during this period should be reported and followed until resolution unless, in the opinion of the investigator, the adverse event or laboratory abnormality/ies are not likely to improve because of the underlying disease.

Table 6: Schedule of Events for Dose Expansion

	Screening	C1				C2				C3			C4-C7			EOT ²² /C8D1	EOS ²³
Day	D-28 to 0	D1	D8	D15	D22	D1	D8	D15	D22	D1	D8	D15	D1	D8	D15	D1	
Window period	-28	0	±1	±1	±1	±1	±1	±1	±1	±1	±1	±1	±1	±1	±1	+7	+30
Study Days	D-28 to 0	1	8	15	22	29	36	43	50	57	64	71	-	-	-	197	227
Informed Consent ¹	X	-	-	-		-	-	-	-	-	-	-	-	-	-	-	-
Demographics ²	X	-	-	-		-	-	-	-	-	-	-	-	-	-	-	-
Medical history ³	X	-	-	-		-	-	-	-	-	-	-	-	-	-	-	-
Vitals ⁴	X	X	X	X	X	X	X	X	X	X	X	X	X	X	X	X	-
Height and weight ⁵	X	X	X	X	X	X	X	X	X	X	X	X	X	X	X	X	-
Complete Physical exam ⁶	X	-	-	-	-	-	-	-	-	-	-	-	-	-	-	X	-
Abbreviated Physical exam ⁶	-	X	X	X		X	X	X		X	X	X	X	X	X	-	-
ECOG Performance Status	X	X	-	-	-	-	-	-	-	X	-	-	-	-	-	X	-
Tumor staging	X	-	-	-	-	-	-	-	-	-	-	-	-	-	-	-	-
Laboratory assessment																	
Complete blood count ⁷	X	X	X	X	X	X	X	X	X	X	X	X	X	X	X	X	-
Chemistry panel I ⁸	X	X	X	X	X	X	X	X	X	X	X	X	X	X	X	X	-
Chemistry panel II ⁹	X	X	-	-	-	-	-	-	-	X	-	-	X	-	-	X	-
Serology ¹⁰	X	-	-	-	-	-	-	-	-	-	-	-	-	-	-	-	-
PT and INR ¹¹	X	X	X	X	X	X	X	X	X	X	X	X	X	X	X	X	-
Urinalysis (routine)	X	X		X		X	-	X		X		X	X		X	X	-
Pregnancy test ¹²	X	X	-	-	-	X	-	-	-	X	-	-	X	-	-	X	-
12-lead ECGs ¹³	X	X	-	-	-	X	-	-	-	X	-	-	X	-	-	X	-
Bone marrow biopsy ¹⁴	X	-	-	-	-	-	-	-	-	-	-	-	-	-	-	-	-

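### Table 5 (dose escalation) leaves blood count, ALT/AST, PT/INR, vital signs and weight unmarked at end of treatment, in conflict with its own footnotes on weight and physical examination and with Table 6

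*Protocol*

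**What the plan says.** Protocol Section 6.13 holds two visit schedules: Table 5 for dose escalation and Table 6 for dose expansion.

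In Table 5 the blood count row runs "Complete blood count ⁷ X X - X X X X X X X X X X X X X". Those 16 cells reach Day 15 of Cycles 4–7; the two that follow, EOT/C8D1 and EOS, are dashes. Chemistry Panel I, which contains ALT and AST (Section 6.4, Table 4), has the same pattern ("Chemistry panel I ⁸ X X - X X X X X X X X X X X X X", then two dashes). So do PT/INR ("PT and INR ¹¹ X X - X X X X X X X X X X X X X", then two dashes), vital signs ("Vitals ⁴ X X - X X X X X X X X X X X X X", then two dashes) and height/weight. Chemistry Panel II is marked at EOT: in "Chemistry panel II ⁹ X X - - - - - - - - X - - X - - X" the final X is the EOT/C8D1 cell.

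Table 6 has no C1D3 column. Its blood count row, "Complete blood count ⁷ X X X X X X X X X X X X X X X X", ends with an X at EOT/C8D1.

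Table 5 marks the complete physical examination at screening and EOS, but its footnote 6 says: "Complete physical examination will be done at screening and EOT visits". Section 6.13 describes the EOS follow-up as a telephone contact. Footnote 5 requires weight at every visit. Section 6.12 states that, apart from patients who move to the compassionate use protocol, "all other patients will undergo the end-of-treatment (EOT) assessments within 7 days after the last dose of study drug". It does not list those assessments.

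**The concern.** Adverse events, including Grade 3/4 events, are the primary endpoint (Protocol 3.1.1), and Section 7.4.3 turns Grade 3/4 laboratory abnormalities into adverse events. An abnormality without symptoms is recorded only if a test is done. If one phase tests at the end of treatment and the other does not, the two phases do not have the same chance of recording such an event. SAP Section 10 places escalation, expansion and Overall columns in the same tables. Escalation may supply up to 18 of 42 patients in the Overall column (18 / (18 + 24) = 43%, if both parts enrol to their stated maximum).

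**Working it through.** **Column alignment.** Table 5 header: screening 1, Cycle 1 five, Cycle 2 four, Cycle 3 three, Cycles 4–7 three, EOT/C8D1 one, EOS one; 1 + 5 + 4 + 3 + 3 + 1 + 1 = 18 columns. Table 6 drops C1D3, leaving 17. Rows in the first part of each table, read against these headers:

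| Row | Table 5 cells | Table 5 EOT | Table 5 EOS | Table 6 cells | Table 6 EOT |
|---|---|---|---|---|---|
| Vital signs | 18 | – | – | 17 | X |
| Height/weight | 18 | – | – | 17 | X |
| Blood count | 18 | – | – | 17 | X |
| Chemistry Panel I | 18 | – | – | 17 | X |
| PT/INR | 18 | – | – | 17 | X |
| Complete physical examination | 18 | – | X | 17 | X |
| Chemistry Panel II | 18 | X | – | 17 | X |

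ECOG status, pregnancy test and ECG in Table 5 also have 18 cells with X at EOT, so no column shift explains the dashes in the other rows.

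**The tables' own study days.** Study day = 28 × (cycle − 1) + day.
- C8D1 = 28 × 7 + 1 = 197, as printed.
- EOS = 197 + 30 = 227, as printed.

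**Length of the gap for a Phase I completer.** From Cycle 3 there is no Day 22 visit, so the last marked blood count, Panel I, PT/INR and vital signs fall at C7D15.
- C7D15 = 28 × 6 + 15 = Day 183.
- Gap to EOT = 197 − 183 = 14 days, or 204 − 183 = 21 days at the end of the +7 window.
- End of Cycle 7 = 28 × 7 = Day 196. Tenalisib is given on Days 1–28 of each cycle (Section 5.1), so 196 − 183 = 13 dosing days follow the last scheduled test.
- In expansion the last scheduled test is at Day 197. The difference between phases is 197 − 183 = 14 days.

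A patient who stops early in escalation has no marked blood count or ALT/AST after the last treatment visit. In expansion the EOT visit provides one.

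**Whether other text fills the gap.** Table 5 footnotes 7, 8 and 11 (blood count, Panel I, PT/INR) give the pre-treatment window and allow extra tests when clinically indicated; none names EOT. Footnote 9 does name C8D1 and EOT, but for Panel II. No section states that the dashed tests are, or are not, done at EOT in escalation, so sites have only the table.

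**Where it enters the analysis.** Adverse event tables (SAP 10.6.2) follow the layout in SAP Section 10, which includes an Overall column. Laboratory values are summarised per cycle within each phase (SAP 10.6.3), so those summaries do not mix the two schedules.

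**The case against.** The strongest reply is that this is a slip in the table, or a fault in reading the PDF, and not a decision to omit tests. That may well be right. Footnotes 5 and 6 contradict two of the rows. Urinalysis in Table 5 moves from Days 1 and 15 in Cycles 2 and 3 to Day 8 alone in Cycles 4–7, unlike Table 6. The rows checked after the page break have one cell fewer than the header in both tables. The rows at issue lie before the break and are complete, but long runs of identical marks can be miscounted. The source PDF must be checked first. If the dashes are there, the conflict needs correcting whatever its origin.

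The second reply is that other provisions protect the patient, and much of this stands. Panel II (with creatinine), urinalysis, ECG and adverse event review remain at the escalation EOT visit. Tests can be added when clinically indicated. Events leading to discontinuation are followed to resolution or stabilisation (Section 7.1.3), although Section 6.13 ends follow-up at 30 days if that comes first. Tables 7 and 8 require repeat testing for several known cytopenias and transaminase elevations. A reader might infer that laboratory toxicity at stopping is ascertained in expansion only; these provisions rule that out. What remains exposed is a new abnormality without symptoms, arising after the last treatment visit.

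Third, a reader might infer that dose selection is at risk. It is not: DLTs are counted in Cycle 1 (Section 7.6), when Table 5 schedules blood count, Panel I and PT/INR on Days 1, 8, 15 and 22.

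**Conclusion.** The inconsistency holds on the printed text: five rows of Table 5 lack an EOT mark that Table 6 has, and a sixth, the complete physical examination, is marked at a telephone contact. Two of the six also contradict Table 5's own footnotes. The consequence is limited. Scheduled blood count and ALT/AST end 14 days earlier for a Phase I completer than for an expansion completer, and an early discontinuer in Phase I has none after the last treatment visit. The likely effect is some under-recording of new, symptom-free Grade 3/4 laboratory events in escalation relative to expansion, carried into the Overall column of the adverse event tables. No hypothesis test is affected, since SAP 9.1 plans none.

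Two larger figures are tempting and should not be used. The time from Day 183 to EOS is 44 of 227 days, but the last 30 have no scheduled laboratory tests in either phase. Protocol 1.1.2 reports 12 treatment-related Grade 3 or higher AST/ALT elevations among 58 patients in an earlier single-agent study (21% if each is a separate patient). That shows why ALT/AST matters here, but it covers the whole of that study and does not measure events first detectable at EOT. The documents give no basis for estimating how many events would be missed.

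This rests on three assumptions: the printed cells match the source PDF; visits fall on nominal days; and completers follow the EOT/C8D1 column. Section 6.12 exempts patients entering the compassionate use protocol from EOT assessments. If that also covers the C8D1 tests, the completer difference applies only to those who do not roll over.

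**What to change.** First check the EOT/C8D1 and EOS columns of Table 5 against the source PDF. If the dashes are there, reconcile Table 5 with its footnotes and with Table 6: mark vital signs, weight, blood count, Chemistry Panel I and PT/INR at EOT/C8D1, and move the complete physical examination mark from EOS to EOT/C8D1.

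If escalation data have already been collected without these tests, add a note beside the adverse event tables with an Overall column, stating that EOT laboratory ascertainment differed between the phases.

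The cost is a table correction by amendment plus one blood count, one Panel I and one PT/INR per Phase I patient, with vital signs and weight, at a visit that already includes a blood draw for Panel II. The physical examination is already required by footnote 6. The note costs one sentence.

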3.4.5.2 Romidepsin

The following adverse events have been reported in patients receiving Romidepsin:

- Myelosuppression: Romidepsin can cause thrombocytopenia, leukopenia (neutropenia and lymphopenia), and anemia; monitor blood counts during treatment with Romidepsin; interrupt and/or modify the dose as necessary.
- Fatal and serious infections, including pneumonia, sepsis, and viral reactivation, including Epstein Barr and Hepatitis B viruses, have been reported in clinical trials with Romidepsin. These can occur during treatment and within 30 days after treatment. The risk of life-threatening infections may be greater in patients with a history of prior treatment with monoclonal antibodies directed against lymphocyte antigens and in patients with disease involvement of the bone marrow.
- Several treatment-emergent morphological changes in ECGs (including T-wave and ST-segment changes) have been reported in clinical studies. The clinical significance of these changes is unknown.
- Tumor lysis syndrome (TLS) has been reported to occur in 1% of patients with tumor stage CTCL and 2% of patients with Stage III/IV PTCL. Patients with advanced stage disease and/or high tumor burden are at greater risk, should be closely monitored, and managed as appropriate.
- Since Romidepsin is a substrate of CYP3A4 enzymes, concomitant administration of CYP3A4 inhibitor or inducer may interact with Romidepsin. If concomitant treatment of these drugs is clinically warranted, careful observation of the patient is advised.

Strong inhibitor or inducers should be avoided as directed in Section on prohibited medication.

Please refer to the full prescribing information of Romidepsin for additional safety information.

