6.4 Laboratory Investigations

Laboratory tests for hematology, chemistry and urinalysis are specified in Table 4.

Table 4: Laboratory Tests for Hematology, Chemistry and Urinalysis

Hematology	Chemistry Panel I	Chemistry Panel II	Urinalysis	Other
Hematocrit	Total bilirubin	Blood glucose	Blood	Serum β -hCG
Hemoglobin	Alkaline phosphatase (ALP)	Urea or blood urea nitrogen ^a	Glucose	Urine pregnancy test
CBC with differentials	Alanine aminotransferase (ALT)	Creatinine	Protein	PT/INR
Platelet count	Aspartate aminotransferase (AST)	Albumin	Specific gravity	Serology (Only at Screening) (Hepatitis B, Hepatitis C, HIV, EBV and CMV)
WBC (Total and differentials)	Lactate dehydrogenase (LDH)	Total protein	Microscopic exam ^b	
Red blood cell count	Gamma-glutamyl transferase (GGT)	Total Cholesterol		
Absolute neutrophil count	Sodium	Triglyceride (TG)		
Absolute lymphocyte count	Potassium	LDL		
	Calcium	HDL		
	Phosphorous	TSH		
	Bicarbonate or Carbon dioxide (CO2)	T3 (Total or Free)		
	Chloride	T4 (free)		
	Magnesium			

^a Blood Urea Nitrogen is preferred; if not available Urea may be tested.

^b Microscopic exam, if abnormal results are noted

Blood drawn for these tests will be specified in informed consent form (ICF). The investigations will be performed at each local laboratory. Additional details will be provided in the study-specific Laboratory Manual.

Screening labs will be done within 7 calendar days prior to the initiation of trial treatment. If these initial examinations are obtained within 72 hours of Cycle 1 Day 1, the labs need not be repeated. Re-screening can be done at the discretion of PI. Scans and other investigations

to document measurable disease should be performed ≤ 28 weeks prior to initiation of treatment.

6.5 12-Lead Electrocardiograms

An ECG will be performed at the time points mentioned below table. Additional ECGs will be obtained if clinically indicated. A single ECG will be performed at all-time points unless specified. Triplicate ECGs only need to be performed at other time points to confirm the significant changes of single ECG (e.g. If QTcF > 450 msec on single EKG at screening or > 500 msec during treatment). All ECGs will be performed on local equipment. Window period of ± 5 minutes will be applicable to 30 min time point. For all time 1 hr time points, ± 15 minutes window period will be applicable.

Dose Escalation		
Days	Time points	Note
Screening	Within last 28 days	-

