8. Chemistry Panel I must be done \leq 7 days prior to C1D1. However, if these initial examinations are obtained within 72 hours of C1D1; they do not have to be repeated. These tests will be performed at supplementary (unscheduled) visits if clinically indicated.
9. Chemistry Panel II must be done \leq 7 days prior to C1D1. However, if these initial examinations are obtained within 72 hours of C1D1; they do not have to be repeated. During treatment, the labs will be performed at C3D1 (\pm 1 days), C5D1 (\pm 1 days) and C8D1 (\pm 7 days) and/ or at the EOT. These tests will be performed at supplementary (unscheduled) visits if clinically indicated.
10. Serology includes HIV, HBV, HCV and CMV. Historical evidence in last 12 weeks is acceptable.
11. PT/INR: PT and INR test must be done \leq 7 days prior to C1D1. However, if initial examination is obtained within 72 hours of C1D1; this do not have to be repeated. In case of abnormality, additional tests including aPTT to be done as per investigator discretion. This test will be performed at supplementary visits if clinically indicated.
12. Pregnancy test is required for women of child bearing potential. A serum/urine pregnancy test will be performed at screening and C1D1 (within 72 hours) of dosing. Urine pregnancy test will be performed at other visits as indicated.
13. 12-lead ECG: PK matching ECG will be done on C1D1 and C1D8. Please refer ECG table for detailed time points. Additional ECGs will be obtained if clinically indicated. Triplicate ECGs will be performed to confirm the significant changes of single ECG. Refer Section 6.5.
14. PK: The blood will be collected for PK on following time points: C1D1: Pre-infusion (0), 1, 2, 3, 5, 7, 9, 10 hrs post-infusion. C1D8: Sampling with respect to Tenalisib dosing. Pre-dose (0), 0.5, 1, 2, 3, 4, 5, 6, 8, 10, 11 post-dose. Pre-dose sample will be taken on C2D1, C3D1 and C4D1. Patient will be hospitalized on C1D1 and C1D8 at the discretion of the site in order to facilitate multiple procedures (e.g. PK blood draws, ECGs) that required to be performed on C1D1 and C1D8. On C2D1, C3D1, C4D1, patients should consume their morning dose at the clinic after the pre-dose sample. Refer Section 6.10.

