7.6.2 Non-Hematological DLTs

- Grade ≥ 3 non-hematologic toxicity that could not be controlled or prevented by supportive care including corticosteroids **with exception of:**
 - Grade ≥ 3 ALT/AST elevation that resolves to \leq Grade 2 within 14 days;
 - Grade ≥ 3 diarrhea that improves \leq Grade 2 within 48 hours **or** Grade ≥ 3 diarrhea in patients who have not received optimal treatment with anti-diarrhoeal drugs.
 - Grade ≥ 3 vomiting in patients who have not received the highest therapeutic dose of antiemetics (e.g. steroids, 5HT3 antagonists, prochlorperazine, lorazepam)
 - Single episode of Grade ≥ 3 infusion reaction.
 - Grade 3 nausea, Grade 3 asthenia or Grade 2 alopecia.
- Treatment delay of ≥ 14 days due to unresolved toxicity.

Adverse events meeting the above definitions but unrelated to study drug will not be considered DLTs. In some instances (e.g. in case of pre-existent Grade 2 toxicity), an event may fall within the protocol definition of a DLT but will not be considered a DLT (i.e., not clinically meaningful/significant or relevant to the combination). In such cases, the SRC will thoroughly review the event, supporting data, and the reasons for not considering the event a DLT will be clearly documented with supporting rationale. Conversely, other events which do not meet the definition of a DLT but are concerning to the SRC may be considered as DLTs.

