7.7.2.1 Tenalisib Dose Modifications for Hematologic Toxicity

The dose modification guidelines are intended to be applied when the investigator determines the events related to Tenalisib.

Table 7: Dose Modifications for Hematologic Toxicity

Worst CTCAE Grade Toxicity	Action to be Taken
HEMATOLOGIC	
Neutropenia (ANC)	
Grade 3 $1.0 \times 10^9 / L < ANC \geq 0.5 \times 10^9 / L$	Maintain dose level. Monitor ANC at least weekly. Restart Tenalisib when the event resolved to \leq Grade 2 or baseline.
Grade 4 $0.5 \times 10^9 / L < ANC$	First incidence: Hold* dose until resolved to \leq Grade 2 or baseline, Restart Tenalisib at one dose lower . Subsequent occurrence: Hold dose until resolved to \leq Grade 2 or baseline, consider growth factor support. Discontinue if further dose modification required.
Grade 3 Febrile neutropenia ANC $< 1000 / \text{mm}^3$ with a single temperature of $> 38.3^{\circ}\text{C}$ (101°F) or a sustained temperature of $\geq 38^{\circ}\text{C}$ (100.4°F) for more than one hour.	Hold* dose until resolved to \leq Grade 2 or baseline, consider growth factor support, then restart Tenalisib at one dose lower .
Thrombocytopenia	
Grade 3 ($50.0 \times 10^9 / L < PLT \geq 25.0 \times 10^9 / L$)	Maintain dose level. Monitor ANC at least weekly. Restart Tenalisib when the event resolved to \leq Grade 2 or baseline.
Grade 4 $25.0 \times 10^9 / L < PLT$ Or thrombocytopenia that requires platelet transfusion	1st occurrence: Hold** dose until to \leq Grade 2 or baseline, Restart Tenalisib at one dose lower. Subsequent Occurrences: Hold dose until to \leq Grade 2 or baseline, consider platelet transfusion as necessary. Discontinue if further dose modification required.

*If study drug is delayed > 2 weeks because of an adverse event, treatment strategy should be discussed with medical monitor.

** Patient receiving concomitant medication (e.g. anticoagulants, anti-platelets, aspirin, or low molecular weight heparin) must be discussed with the medical monitor for continued management.

Table 8: Dose Modifications for Non-Hematologic Toxicities

NON-HEMATOLOGIC	Action to be Taken
Renal*	If serum creatinine is Grade 3 ($> 3 \times$ baseline or $> 3 \times$ ULN), hold dose until \leq grade 2. Monitor serum creatinine at least twice a week until resolution to \leq grade 2, and then at least one week until it resolves to \leq grade 1.

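### No creatinine is scheduled between C1D1 and C3D1 (Day 57), so an asymptomatic creatinine-defined DLT or Table 8 renal hold could go unmeasured

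*Protocol*

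**What the plan says.** **Which panel.** Protocol Section 6.4 states that "Laboratory tests for hematology, chemistry and urinalysis are specified in Table 4". One row of that table reads across as "Alanine aminotransferase (ALT) Creatinine Protein". The columns there are Panel I, Panel II and urinalysis, so creatinine is a Panel II test. Urea/BUN is in the same column. The SAP Section 10.6.3 table has a different row order and also lists both under Panel II.

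**When it is drawn.** The row "Chemistry panel II ⁹" in Tables 5 and 6 is marked at screening and C1D1, is empty at every later Cycle 1 visit and every Cycle 2 visit, and is marked again at C3D1. Footnote 9 of both tables says "During treatment, the labs will be performed at C3D1", then C5D1 and C8D1 and/or EOT. In Table 5 it adds: "These tests will be performed at supplementary (unscheduled) visits if clinically indicated". Table 6 has an equivalent sentence.

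**What depends on it.**
- Protocol Section 7.6.2 counts as a DLT a Grade 3 or higher "non-hematologic toxicity that could not be controlled or prevented by supportive care including corticosteroids". Creatinine is not among the listed exceptions.
- Section 7.6.3 runs the DLT window from C1D1 to C2D1.
- The renal row of Table 8 holds Tenalisib at Grade 3 creatinine and then requires: "Monitor serum creatinine at least twice a week until resolution".

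**The concern.** Establishing the MTD is a primary objective, and Section 3.2.1.1 makes the first 28 days of safety data essential to each escalation decision. One DLT definition and one dose-hold rule can turn on serum creatinine, yet the schedule supplies no creatinine after dosing starts until four weeks after the DLT window has closed. Section 7.4.3 requires Grade 3 or 4 laboratory abnormalities to be recorded as adverse events, but an abnormality that is not measured cannot be recorded.

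The cohorts are small. In a 3+3 design, one event decides whether a three-patient cohort escalates (0 of 3) or is expanded (1 of 3). It also decides whether a six-patient cohort escalates (1 of 6) or exceeds the MTD (2 of 6). A site could follow the plan exactly and still report a cohort as free of renal DLT because renal function was not measured.

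**Working it through.** The check is calendar arithmetic plus a count of scheduled draws.

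**1. Reproduce the study days.** Study day = (cycle − 1) × 28 + day.
- C2D1 = 1 × 28 + 1 = 29
- C3D1 = 2 × 28 + 1 = 57
- C8D1 = 7 × 28 + 1 = 197

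All three match the study-day row of Tables 5 and 6.

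**2. Scheduled creatinine to C3D1.** The Panel II days are 1 and 57. The number falling after Day 1 and up to Day 29 is zero.

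**3. Length of the gap.**
- Planned: 57 − 1 = 56 days.
- With the ±1 day window that footnote 9 gives for C3D1: 55 to 57 days.
- If the C1D1 draw is waived because screening tests were done within the previous 72 hours: up to 57 + 3 = 60 days.
- From the end of the DLT window to the first scheduled on-treatment value: 57 − 29 = 28 days.

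**4. Romidepsin infusions before Day 57.** Days 1, 8, 15, 29, 36 and 43, so six. Day 1 has its own Panel II draw (or one within the preceding 72 hours). The number with no same-visit creatinine is 6 − 1 = 5.

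**5. Draws already planned.** Panel I is marked on Days 8, 15, 22, 29, 36, 43 and 50, so seven between Day 1 and Day 57. Four (Days 8, 15, 22, 29) fall in the DLT window if C2D1 is counted, as Section 7.6.3 does. Three do so if the window is read as closing on Day 28.

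**6. After C3D1 the sources disagree.**

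| Source | Panel II days from C3D1 | Gaps (days) |
|---|---|---|
| Footnote 9 | 57, 113, 197 | 56, 84 |
| Grids of Tables 5 and 6 (Day 1 of Cycles 4-7 marked) | 57, 85, 113, 141, 169, 197 | 28 each |

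Before C3D1, grid and footnote agree, so the result for Days 2 to 56 does not depend on which is followed.

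**The case against.** **Unscheduled tests are allowed.** Footnote 9 permits them and does not require symptoms. Section 6.1 also lets the investigator add procedures judged clinically necessary. An abnormal Panel I value or urinalysis could be the prompt, and urinalysis is scheduled on Days 15 and 29. This reduces the gap, but it needs a prompt. An isolated creatinine rise without symptoms may give none, and electrolytes or urine protein cannot grade creatinine under Table 8.

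**The prior evidence of renal toxicity is thin.** Protocol Section 1.1.2 lists treatment-related Grade 3 or higher events among 58 patients on Tenalisib, and none is renal. Section 1.1.1 names thyroid and liver as the target organs. Entry requires creatinine clearance above 50 ml/min. A DLT must also be related to the combination and not controlled by supportive care. All of this stands and lowers the likely frequency of a missed event. However, the Section 1.1.2 list may be incomplete, and the study behind it did not test the combination.

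**Stronger readings that the documents do not support.**
- A reader might infer that early tumor lysis cannot be detected, since Section 3.4.5.2 warns that "Tumor lysis syndrome (TLS) has been reported to occur in 1% of patients with tumor stage CTCL". But Panel I carries potassium, calcium, phosphorous and LDH weekly from Day 8 through Cycle 2, so the electrolyte signs are on schedule. Only the creatinine and urea component is missing.
- A reader might infer that any renal DLT would be missed. Symptomatic events and Grade 3 electrolyte changes can still surface through Panel I and adverse event review.
- A reader might take the later gaps of 56 and 84 days as fact. They follow from footnote 9 alone, and the grids contradict it.
- Uric acid is in no panel, but nothing in the documents calls for it.

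**Conclusion.** The point holds for creatinine and urea/BUN between C1D1 and C3D1, in both parts of the study. The DLT window has no scheduled post-dose creatinine, and the Table 8 renal rule has no scheduled input for 56 days (up to 60 if the C1D1 draw is waived). Six infusions precede the first scheduled on-treatment value. What could be missed on scheduled tests is an asymptomatic, creatinine-defined DLT or renal hold.

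The conclusion rests on the panel lists in Table 4 and the SAP, which agree, and on the grids and footnote 9, which agree up to C3D1. It assumes that sites draw what is scheduled and add creatinine only when something prompts it. The documents give no rate of creatinine events for the combination, so the chance that a missed event changes an escalation decision cannot be estimated. The plan should still be amended, because the gap bears on a primary objective and the remedy is small. The renal hold rule itself is not in question, only whether the schedule supplies its input.

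**What to change.** List creatinine and urea/BUN under Chemistry Panel I in protocol Table 4 and in the SAP Section 10.6.3 table. They would then run on blood already drawn on Days 8, 15, 22, 29, 36, 43 and 50. Lipid and thyroid tests can stay in Panel II.

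Keep a creatinine at C8D1/EOT when making the change. As Table 5 reads, the Panel I row has no mark at that visit, while Table 6 does, so a straight move could drop it in the escalation part.

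Separately, reconcile the Panel II grid (Day 1 of Cycles 4-7) with footnote 9 (C5D1 and C8D1 only) in both tables.

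The cost is a short amendment to the two laboratory tables and footnote 9, plus a few more analytes per existing sample. No visit or venepuncture is added.
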